Visit#6: Follow-up (one month); END of STUDY.

Study Population: Sixty-five non-treatment-seeking, alcohol-dependent participants will be recruited. Fifty-eight participants will be enrolled for screening with **50 participants (n = 50)** expected to complete the study. Participants will primarily be recruited via advertisements placed in local newspapers and posted on buses.

Safety Measurement/Parameters: Risks of medication side effects will be minimized through careful and detailed screening of participant. Signs of anxiety and stress, adverse events and vital signs will be assessed at each visit by psychometric assessments. Safety laboratory tests will be evaluated at baseline, and at the end of the study participants will receive a behavioral motivational session at the end of Visit 5.

Financial considerations: There will be no cost(s) to participate in this study. The study medications and all procedures that are not part of routine care, but are required for the study, will be provided to the participant. If eligible for the study, participants will receive \$25 for the randomization visit (Visit# 2) and for the follow-up visits (Visits #4 and #6). During the laboratory phase, at each visit (Visits #3 and #5) participants are compensated \$100 + another possible \$3/drink as incentive for not drinking (max \$24). Therefore, each participant may be compensated up to \$323 during the entire study period. Participants will be also compensated for their travel costs.

Specific Aims:

Aim 1: to assess the safety and tolerability of mifepristone and yohimbine while consuming alcohol.

Aim 2: to test the hypothesis that an increase in alcohol craving induced by yohimbine is antagonized by pre-administration with mifepristone.

Aim 3: to test the hypothesis that an initial priming drink and alcohol consumption induced by yohimbine is antagonized by pre-administration with mifepristone.

TABLE OF CONTENTS

PROTOCOL SYNOPSIS	2
TABLE OF CONTENTS	3
SPECIFIC AIMS	4
RATIONALE AND SIGNIFICANCE TO THE ALCOHOL FIELD	5
Stress and alcohol dependence	5
Clinical relevance	5
Pharmacological stress targets	5
Mifepristone	5
Stress-induced models	6
Integration: psychoneuroendocrinology and trauma factors	6
Significance for NIAAA	6
Innovation	6
The Investigator Team	7
The qualified medical personnel during the laboratory sessions	7
RESEARCH DESIGN AND METHODS	8
Overview of Proposed Research	8
Medications and Doses	8
Study Procedures	9
Data Analysis Plan	10

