
PharmD with the double track in Pharmaceutical Science at UCSF, School of Pharmacy (#1 Pharmacy School in the US). She performed research at the prestigious Ernest Gallo Clinical and Research Center in California under the mentorship of [name], now one of the top directors at NIH. This high selective doctoral program allowed her to receive a double concurrent appointment at UCSF in the Neuroscience Department (Gallo Center) and in the Department of Clinical Pharmacology and Experimental Therapeutics (School of Medicine).

[figure not shown]
The study physician, either [name], will be present during the screening visit. They will perform the physical exam and psychological assessments. [name], is a practicing physician and is Board Certified in Addiction Psychiatry. [name] is Staff Psychiatrist at the VA Medical Center at Roger Williams Medical Center and at CAAS; he has extensive alcohol laboratory experience and contributed to the advancement of knowledge in the AUD research field through several selected publications^{23,70-86}. [name] and the RA will immediately call the study physician if any safety issues arise during or between sessions (i.e. CIWA score ≥ 7).

[name] has the support of Research Associates (RA) who have been trained in administering psychological assessments (i.e. CIWA, SCID, HAM-D/A), conducted similar alcohol and pharmacological studies for many years at Brown and included in our peer-review. They also will collect blood, saliva and urine samples and monitor blood pressure and heart rate using a Dinamap Adult Vital Signs Monitor.

METHODS

Overview of Proposed Research. The design will be a randomized within, crossover, double-blind, placebo-controlled human study with mifepristone in non-treatment-seeking alcohol-dependent individuals. The study will be conducted in two consecutive phases with one month washout period (**Figure 1**): Visit #1, Screening; Visit #2: randomization and drug/placebo dispensed; Visit #3: first lab-session: single dose of yohimbine; Visit #4: After one-month washout period (**30 days, plus or minus two days to accommodate the schedule of the next visit**), follow-up and drug/placebo dispensed; Visit #5: second lab-session, single dose of yohimbine, motivational session (MET); Visit #6: follow-up (one month). END of STUDY.

Figure 1 – Study Design

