Alcohol Self-Administration (ASA). Participants are presented with a priming dose of alcohol designed to raise blood alcohol levels to 0.03 g/dl. Consistent with previous studies^{78,103,104}, we will wait 40 minutes before presenting more alcohol. We will assess craving and whether stress-induced craving will modify responses to the priming drink using the ACQ. Stimulant and sedative effects of alcohol will be assessed using the Biphasic Alcohol Effects Scale (BAES)¹⁰⁵. The "free-choice" phase of the ASA lasts 120 min and the ACQ will be

administered every 30 min^{78,103,104,106}. Each participant will get \$3.00 per drink (max possible is \$24), provided as an alternative reinforcer for not drinking. Each beverage is calculated to raise the blood alcohol levels by 0.015g/dl. If the participant's BrAC has reached 0.1, then the alcohol consumption period will stop. We will also collect multiple BrAC values in order to monitor the mifepristone effects on alcohol pharmacokinetic and pharmacodynamic levels. Participants wait until BrAC = 0.00 (repeated twice) before being discharged. At the end of Visit 5, a Motivational Enhancement Therapy (MET) will be performed to provide education about alcoholism and to explore participants' desire to get treatment if they wish to receive it, and then we will assess at last follow-up to ascertain that drinking has not increased.

Participants are strongly encouraged to remain in the lab until no longer intoxicated. After the laboratory session, we will provide food and water and they can watch television. If they want to leave, we will provide a taxi ride.

Compensation: sessions will last approximately 6 hours, and subjects will receive \$100 for participation plus another possible \$3/drink as incentive for not drinking (max \$24).

Washout period: During the washout and follow up period (30 days, plus or minus two days to accommodate the schedule of the next visit) we will contact participants weekly by telephone to ensure that there are not unexpected side effects. We will alert the study physicians in the event of anxiety, depression and suicidality. We will also send a text reminder for the next visit (Visit #4 and Visit #6).

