Secondary outcomes: Craving measures included alcohol craving questionnaire short form-revised (ACQ-SF-R)². Values of the water trials for each dependent variable were inserted as covariate in the model (allowed for the dependent variable to be specific for alcohol), time coded: t_1 =alcohol trial 1 and t_2 =alcohol trial 2. In the bar laboratory, alcohol consumption was measured by number of drinks consumed (*t*-test). In the outpatient setting, alcohol consumption was measured by self-report using the timeline follow back method, reported as heavy drinking days and drinks per week.

All statistical analysis was performed after participants had their follow-up visit and the study database had been locked. All the statistical procedures were performed by IBM SPSS Statistics for Windows, version 27 with Macro MEMORE extension⁹ (IBM Corp., Armonk, NY, USA) and GraphPad Prism (v.5) was used to generate figures (La Jolla, CA, USA). The effect sizes were calculated as η^2 for GLM and Cohen *d* for *t*-test. All statistical tests were two-tailed, and statistical significance was accepted if an alpha value $p<.05$ was obtained.

For all outcomes, we utilized an intention-to-treat (ITT) approach, where participants were examined based on their *a priori* randomized protocol and received at least one dose of the study medication

(mifepristone or placebo)³. All analyses were conducted using Generalized Estimating Equations (GEE)⁴ with robust standard errors, and an unstructured correlation matrix, unless noted.

Power

This was a proof-of-concept trial to demonstrate the feasibility of the combined study design, the safety and tolerability of mifepristone and yohimbine while consuming alcohol, and the potential value of testing mifepristone in an appropriately-powered larger RCT. In selecting a target sample size, we balanced power considerations and feasibility given the translational nature of this trial. Because of the within-subjects design, power to test the effects of study drug is optimized for this modest sample size (originally $N=20$ then, after additional funding, increased to $N=32$). For the safety and tolerability outcomes (primary) adverse events difference was detected based on a judgement concerning the minimal effect which has clinical relevance in the management of patients. In a noninferiority trial, the exact sample size cannot be fixed in advance because it depends upon the chosen stopping guideline⁵.

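### The default GEE analysis has no small-sample correction specified for 32 participants, so its nominal 5% tests would run at about 6–10% for the models the SAP describes if the usual uncorrected Wald test is used

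*SAP*

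**What the plan says.** The SAP, in its Statistical analysis section, runs all analyses by GEE "with robust standard errors, and an unstructured correlation matrix, unless noted". On testing it says "All statistical tests were two-tailed" and "statistical significance was accepted if an alpha value $p<.05$ was obtained". Its Power section gives the sample size as "originally $N=20$ then, after additional funding, increased to $N=32", without saying whether 32 counts participants enrolled, dosed or completed, and with no effect size, SD or power behind it.

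The SAP names exceptions to GEE. The number of adverse events is compared by chi-square, as the other safety measures apparently are, and drinks consumed in the bar laboratory by t-test. The one repeated-measures model it describes is cue-reactivity craving: two alcohol trials per condition, coded as time, with the water-trial value as covariate. It names SPSS version 27 but no GEE options, fallback correlation structure or rule for non-convergence.

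The protocol's Overview of Proposed Research describes a "randomized within, crossover, double-blind, placebo-controlled human study with mifepristone", so each participant is one cluster. The synopsis gives 50 participants "expected to complete the study". The protocol's Data analysis section plans paired t-tests, ANCOVA and repeated-measures ANOVA, and keeps GEE for rare dichotomous events.

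**The concern.** The sandwich variance is built from residuals that the fitted model has already made too small. With many clusters this does not matter. With about 30 it makes the standard error too small on average, and a normal or chi-square reference then ignores the remaining uncertainty in that standard error. An unstructured matrix adds parameters: m values per person need m(m−1)/2 correlations, which is 6 for the craving model (m=4), 28 for m=8 and 45 for m=10.

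What is at stake is the meaning of 0.05 for the GEE outcomes. A craving or drinking result just under that level would be weaker evidence than it appears, in a trial meant to judge whether mifepristone deserves a larger study.

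**Working it through.** **Inputs from the documents.** Two-sided alpha 0.05, critical value 1.96; N=32 (SAP), with 20 (the SAP's original target) and 50 (the protocol's expected completers) as the range; two periods; two alcohol trials per period in the craving model.

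**Assumptions not in the documents.** Gaussian outcomes, correlation 0.7 within and 0.5 between conditions, balanced sequences, no missing data, uncorrected Wald test. Each simulation cell used 3,000–5,000 runs unless noted, with Monte Carlo error of about ±0.7 to 1.2 points.

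**Plan's own figure.** The Wald test delivers 5% only as the number of clusters grows without limit. The question is how far from that N=32 lies.

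**Step 1: one value per period (exact).** The robust GEE test is then a paired test whose variance is divided by n, referred to a normal distribution.
- No period term: size = P(|t(n−1)| > 1.96·√((n−1)/n)). At N=32, 1.96·√(31/32) = 1.929, and P(|t(31)| > 1.929) = 6.3%.
- With a period term: size = P(|t(n−2)| > 1.96·√((n−2)/n)). At N=32, 1.96·√(30/32) = 1.898, and P(|t(30)| > 1.898) = 6.7%.
- The same formulas give 7.1% and 7.9% at N=20, and 5.8% and 6.1% at N=50.

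Simulation at N=32 gave 6.5%, in agreement.

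**Step 2: craving model (four values per person, unstructured).** Separate simulations at N=32 gave 7.8%, 8.3%, 8.5% and 9.7%. Their set-ups were not identical, so the spread is not all simulation error. The lowest figure includes treatment, period, time and the water covariate. The same set-up gave 10.1% at N=20 and 7.0% at N=50. If 32 were the number enrolled and the protocol's expected completion applied, 32 × 50/58 = 27.6, about 28 completers, where it gave 8.1%.

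**Step 3: longer series (an assumption).** The protocol's Alcohol Self-Administration subsection has the ACQ "administered every 30 min" over 120 minutes. That would be four or five values per session, or 8–10 per person. The SAP gives no model for them. With an unstructured matrix at N=32, simulations of eight values gave 9.4% to 14.2%, and of ten values 11.8%.

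**Step 4: how much comes from the unstructured matrix.** Uncorrected tests at N=32 with an exchangeable matrix gave 7.9% for the craving model, against 7.8% unstructured, and 6.8% for ten values, against 11.8%. The matrix matters mainly for the longer series. For the craving model the main cause is the uncorrected variance and its normal reference.

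**Step 5: does a correction work?** Mancl-DeRouen variance with a t(n−p) reference, N=32:

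| Values per person | Working matrix | Size |
|---|---|---|
| 2 | unstructured | 3.9% |
| 4 (craving) | unstructured | 4.6% |
| 4 (craving) | exchangeable | 5.0% |
| 8 | unstructured | 6.1% |
| 10 | unstructured | 8.3% |
| 10 | exchangeable | 4.2% |

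Other runs gave 3.7–5.8% for two to four values. For long series with an unstructured matrix the correction alone was not enough (up to 10.3%).

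**The case against.** The strongest reply is that the excess is modest and confined to secondary outcomes of a self-described proof-of-concept trial. Much of that stands. Several stronger readings are tempting and should be set aside.

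- **That every test is affected.** A reader might infer this because GEE is the default and 0.05 applies throughout. The default carries an exception clause, and the primary adverse-event comparison and laboratory drinks have other tests named.
- **That the standard errors were uncorrected.** This is inferred from silence. The SAP says only that they are robust.
- **That error rates of 9–14% apply.** They belong to a longer series that joins the protocol's ACQ schedule to the SAP's default. The SAP's time coding covers only the two cue-reactivity trials.
- **That the unstructured matrix would often fail.** One simulation of eight values found a usable matrix in only 1,989 of 4,000 data sets. The count depends on how the correlations are estimated: a residual correlation matrix was usable in 3,000 of 3,000 runs and a moment estimator in 19 of 3,000. It is not a property of the plan.
- **That the next study would be mis-sized.** Standard errors that are too small do not bias point estimates, and the SAP's effect sizes are eta-squared for GLM and Cohen d for t-tests. The link is not shown.
- **That dropout after period 1 biases GEE.** The SAP states no missing-data assumption, but the documents give no count of such participants, so no size can be attached.

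What the reply does not answer is that the SAP's default, followed in its usual form at this sample size, does not deliver the significance level the SAP claims.

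**Conclusion.** The point holds as a moderate, fixable gap in specification. If the usual uncorrected Wald test is used at N=32, the nominal 5% test of mifepristone versus placebo has a real size of about 6–7% with one value per period. For the craving model described it is about 8–10%, up to roughly twice the stated rate. A range of 9–14% is conditional on fitting eight or more values with an unstructured matrix. Fewer completers would raise these figures; the protocol's 50 would lower them without removing the excess.

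The one-value result is exact under normality and balanced sequences. The others rest on the assumed correlations, Gaussian outcomes and complete data. Binary or skewed outcomes, which heavy drinking days may be, were not simulated, so for those the direction is expected but the size is not established.

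**What to change.** For the analyses that stay with GEE, state in the SAP:
- a bias-corrected sandwich variance (for example Mancl-DeRouen) with a t reference and its degrees of freedom;
- an exchangeable working matrix, at least for any series longer than the craving model;
- which outcomes are analysed by GEE, and how many values per person each model contains.

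Alternatively, for continuous outcomes, use a linear mixed model with condition, period and sequence, a random subject effect, and Kenward-Roger or Satterthwaite degrees of freedom. Add a subject-by-period random effect only where there are several values per period; with one value it cannot be separated from residual error.

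The cost is SAP wording and a re-run of the affected secondary analyses, with slightly larger p-values and wider intervals. It may also need software beyond a default SPSS GEE run, since the documents do not show that the correction is available there. If a correction was in fact applied, naming it closes the question for the craving model. For any longer series, the working matrix must be stated as well.
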